#### **7.6.4      Eastern Cooperative Oncology Group Performance Status**

ECOG performance status ([Appendix 1](#)) will be collected and recorded on the eCRF at the baseline visit, scheduled 6-month M0 Phase study visits, M0 Phase imaging visits, and time points for data collection in M1 Phase.

#### **7.6.5      New Sites of Metastases**

At all M1 data collection time points, new sites of visceral, nodal or bone metastases will be recorded on the eCRF.

#### **7.6.6      Height and Weight**

Height and weight will be measured at the baseline visit and recorded on the eCRF.

#### **7.6.7      Adult Comorbidity Evaluation**

The ACE-27 ([Appendix 2](#)) is used to identify the important medical comorbidities and determine the overall comorbidity score. For all patients, clinic staff will complete the ACE-27 at the baseline visit. For those patients who enter M1 Phase because of a positive imaging study during M0 Phase, an ACE-27 is required to be completed within 6 months after the patient's last M0 Phase visit.

#### **7.6.8      Gleason Score**

At the baseline visit, Gleason scores from initial prostate cancer diagnosis and, if available, following grade change after RP, will be collected and recorded on the eCRF. The highest and second highest values will be recorded.

#### **7.6.9      Prostate-specific Antigen History**

At the baseline visit, all serum PSA values, as available, from the date of diagnosis with CRPC as defined in the protocol until the date written informed consent is obtained will be recorded on the eCRF. Serum PSA values documented in a medical record are acceptable.

#### **7.6.10     Current Opioid Analgesic Use**

At the baseline visit and all M0 and M1 data collection, current opioid use (yes/no) will be recorded on the eCRF.

#### **7.6.11     Concomitant Medications**

At the baseline visit, the patient's current prescription medications and indications will be recorded on the eCRF. Only prescription medications will be recorded.

### **7.6.12 Pain Status**

At the baseline visit, scheduled 6-month M0 Phase study visits and M0 Phase imaging visits, pain status will be measured with the BPI ([Appendix 3](#)) and the information will be recorded on the eCRF.

### **7.6.13 Prostate Cancer Interventions**

At the baseline visit, all previous and ongoing prostate cancer interventions will be recorded. From registration until the patient is discontinued from or completes the study, all prostate cancer interventions will be recorded on the eCRF. Prostate cancer interventions include but are not limited to radiation, chemotherapy, hormonal therapy, investigational cancer therapies, all other systemic therapies (including steroids), and surgery for prostate cancer. Information collected regarding prostate cancer interventions will include the indication(s) for choice of therapy, starting dose, timing (start and stop dates), and rationale for starting and stopping therapy (e.g., PSA progression).

### **7.6.14 Survival Status**

Survival status is assessed in patients at all M0 and M1 data collection time points. The terms “alive” with the date of confirmation, “deceased”, or “unconfirmed” are collected. For those patients recorded as “deceased”, an additional eCRF page entitled “Date and Cause of Death” will become available. On this page, “Date of death” and “Cause of Death (check all that apply): Disease progression, Cardiac event, New primary cancer, Cerebrovascular event, and other (specify)”, are listed as choices.

### **7.6.15 Imaging Studies**

Patients will undergo bone imaging studies (e.g., MRI,  $^{99m}\text{Tc}$  bone scintigraphy or  $^{18}\text{F-NaF}$  PET/CT) and soft tissue imaging studies (e.g., contrast-enhanced abdominal and pelvic CT or MRI) at the baseline visit and M0 Phase visits in order to detect any M1 disease. The imaging modality will be determined based on the study site’s standard of care and will be recorded on the eCRF.

The presence of M1 disease will be determined by the presence of bone, regional or distant nodal, or visceral metastasis, as follows:

- **Bone metastasis**

Patients with one or more unequivocal bone lesions as identified by site’s standard for imaging modality will be considered to have M1 CRPC. Patients with equivocal scans determined by standard imaging (e.g.,  $^{99m}\text{Tc}$  bone scan) will be evaluated by more sensitive imaging modalities such as CT,  $^{18}\text{F-NaF}$  PET/CT, or MRI within 1 month of the equivocal scan to confirm M1 disease status ([Adams 2011](#)).

- Regional or distant nodal metastasis

Patients diagnosed with lymph node(s) (measuring  $\geq 2$  cm on the greatest diameter) in either regional pelvic or distant lymph nodes will be considered to have M1 disease (Scher 2008).

Examples of regional lymph nodes include: hypogastric, obturator, internal and external iliac and lateral, presacral and promontory sacral lymph nodes (Adams 2011).

Examples of distant lymph nodes, which lie above the bifurcation of the common iliac arteries and outside of the confines of the true pelvis, include: aortic, common iliac, deep inguinal, superficial inguinal, supraclavicular, cervical, scalene, and retroperitoneal lymph nodes (Adams 2011).

- Visceral metastasis

Patients diagnosed with metastasis to liver, lung, brain, or other solid organ will be considered to have M1 disease.

The number and sites of bone, regional or distant nodal, or visceral metastases, if present, will be recorded on the eCRF.

The same bone and soft tissue imaging modalities utilized at baseline should be used for all images for a given patient until diagnosis of M1 CRPC. However, the imaging modality may be changed at the investigator's discretion, assuming that subsequent imaging studies are performed with the new modality. If the diagnosis of M1 CRPC occurs during the first use of a new imaging modality (e.g., first use of  $^{18}\text{F}$ -NaF PET/CT imaging after previous use of  $^{99\text{m}}\text{Tc}$  bone scintigraphy), an additional imaging study with the previous imaging modality will be performed within 1 month after the positive imaging study to allow comparison of the sensitivity and specificity of the 2 methods; this additional imaging study will be reimbursed by the sponsor. However, if the change is from a higher to a lower sensitivity modality, the higher sensitivity modality will not be repeated.

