### M0 Phase

During the M0 Phase, there are 2 types of visits. Post-baseline imaging studies are not required in the M0 Phase and are performed if the investigator determines imaging study(ies) is/are needed to assess development of metastases (M1 CRPC). Depending on the timing of an imaging study, its results may be recorded as part of the 6-month M0 Phase study visit or part of an M0 Phase imaging visit, as described below:

- **6-month M0 Phase study visit:** A scheduled 6-month M0 Phase study visit (office visit), will occur every 6 months ( $\pm$  1 month), starting from the date of the patient's registration, until 3 years after the last patient is registered. Any imaging study that occurs within 1 month of a 6-month M0 Phase study visit will be considered part of that 6-month M0 Phase study visit, and no repeat study assessments will be required.
- **M0 Phase imaging visit:** This visit occurs if, outside of the 1-month window for the 6-month M0 Phase study visit, the investigator determines imaging study(ies) is/are needed to assess development of metastases (M1 CRPC).

The choice of imaging modality will depend on the study site's standard of care; the same modality should be used for all images for a given patient until diagnosis of M1 CRPC. However, if the modality is changed to one with greater sensitivity (e.g., Tc 99m to NaF PET/CT or MRI) and diagnosis of M1 CRPC occurs at first use of a new imaging modality, an additional imaging study with the previous modality will be performed within 1 month after the positive imaging study; this additional imaging study will be reimbursed by the sponsor. However, if the modality is changed to one with lower sensitivity, an imaging study with the previous higher modality will not be performed.

Assessments for both types of M0 Phase visits include: ECOG performance status, current opioid analgesic use (yes/no), pain status (with BPI), prostate cancer interventions since the previous visit, survival status, blood samples for clinical laboratory tests (alkaline

phosphatase, hemoglobin, LDH, serum albumin, and serum PSA) and for AOR (if patient has consented to AOR), and safety events (serious adverse events [SAEs], see Safety Measures, below); all such data that have become available since the previous visit will also be collected.

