- d For those patients who enter M1 Phase because of a positive imaging study at a 6-month M0 Phase study visit or an M0 Phase imaging visit, clinic staff will complete the ACE-27 within 6 months after the patient's most recent M0 Phase study visit and not at other time points.
- e All serum PSA values from the date of diagnosis with CRPC until the date of written informed consent, where available, will be recorded on the eCRF.
- f Prostate cancer interventions include but are not limited to radiation, chemotherapy, hormonal therapy, investigational cancer therapies, all other systemic therapies (including steroids), and surgery for prostate cancer. Record indication(s) for choice of therapy, starting dose, timing (start and stop dates), and rationale for starting and stopping therapy on the eCRF.
- g The number and sites of bone, regional or distant nodal or visceral metastases, if present, will be recorded on the eCRF. Choice of imaging modality depends on study site's standard of care; the same modality should be used for all images for a given patient until diagnosis of M1 CRPC. However, if modality is changed and diagnosis of M1 CRPC occurs during first use of a new imaging modality, an additional imaging study with the previous modality will be performed within 1 month of the positive imaging study; this additional imaging study will be reimbursed by the sponsor. However, if the change is from a higher to a lower sensitivity modality, the higher sensitivity modality will not be repeated.
- h Frequency of imaging studies will be at investigator's assessment of need. Imaging studies performed within 1 month of a 6-month M0 Phase study visit will be considered part of that visit.
- i For patients in M1 Phase, clinical laboratory results, including serum PSA data, that have become available since the previous time point for data collection will be recorded on the eCRF.
- j For patients who receive at least 1 partial ( $>0$  mL) infusion of Provenge, record SAEs that occur  $\leq 30$  days after the last infusion, regardless of relationship to Provenge.

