### **8.3.2 Secondary Endpoints**

The proportion of patients who receive a diagnosis of M1 CRPC at the time of the baseline imaging study will be categorized as metastatic due to soft tissue (nodal and/or visceral) metastases, bone metastases, or both. The percentage of patients in each category will be computed based on the primary analysis population.

Logistic regression analyses, similar to the analyses described for the primary endpoint, will be used to identify characteristics predictive of an imaging study positive for M1 in the M0 population. Analyses will be performed using baseline information only as predictor variables with the outcome variable as a positive imaging study (yes/no) at any post-baseline time point. In addition, an analysis will be performed on the M0 population using all imaging studies collected in the study as the outcome variable (positive=yes/negative=no) with predictor variables associated with each imaging study. Appropriate methods accounting for the correlation of multiple studies for a patient, such as generalized estimating equations, will be used for this analysis. Cox regression analyses incorporating information on the time to occurrence of a positive imaging study will be performed to supplement these analyses.

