### **8.3.3 Exploratory Endpoints**

Prostate cancer treatment practice patterns will be summarized descriptively for patients with M0 CRPC and M1 CRPC. Prostate cancer interventions prior to study entry will be summarized. Additionally, the timing and sequence of prostate cancer interventions during the study will be summarized.

The identification of biomarkers in the M0 population that are predictive of an imaging study positive for M1 will be performed using logistic regression and Cox regression, as previously described. These analyses will be performed for both the primary endpoint (a positive imaging study at baseline) and the endpoint of a positive imaging study at any post-baseline time point.

The percentage of patients with CRPC with previously undiagnosed M1 at baseline will be calculated as 100 times the number of patients in the M1 analysis population divided by the total number of patients in the study.

Logistic regression analyses will be used to determine patient characteristics in the M0 population that are predictive of a positive imaging study at baseline as detected with different imaging modalities. The differing imaging modalities include MRI, 99mTc bone scintigraphy, or F-NaF PET/CT for bone imaging; and contrast-enhanced abdominal and pelvic CT or MRI for soft tissue imaging. For each imaging modality, multivariate logistic regression modeling will be used to identify factors that are independently predictive of a positive imaging study. These analyses will be performed for both the primary endpoint (a positive imaging study at baseline) and for the endpoint of a positive imaging study at any post-baseline time point.

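### The repeat scan on the previous modality follows only a positive first use of a new one, so it can give concordance among positives but not sensitivity or specificity, and Section 8 has no rule for it

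*Combined protocol and SAP*

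**What the plan says.** **Trigger and purpose.** Section 7.6.15 sets the condition "If the diagnosis of M1 CRPC occurs during the first use of a new imaging modality"; then "an additional imaging study with the previous imaging modality will be performed within 1 month after the positive imaging study". The stated reason is "to allow comparison of the sensitivity and specificity of the 2 methods". There is one exception: "if the change is from a higher to a lower sensitivity modality, the higher sensitivity modality will not be repeated". Section 4.0 (M0 Phase) has the same trigger, "diagnosis of M1 CRPC occurs at first use of a new imaging modality", and so does Table 1, footnote g: "if modality is changed and diagnosis of M1 CRPC occurs during first use of a new imaging modality".

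**What counts as M1.** In 7.6.15, M1 is the site's own imaging result: an unequivocal bone lesion by the site's standard, a node of at least 2 cm, or a visceral metastasis. No separate standard of truth is named.

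**Analysis.** Section 8.3.2 models baseline predictors "with the outcome variable as a positive imaging study (yes/no) at any post-baseline time point". It adds a second model in which each scan in the M0 population is an outcome record, with a method such as GEE for within-patient correlation, and supplementary Cox regression. Section 8.3.3 says "For each imaging modality, multivariate logistic regression modeling will be used to identify factors that are independently predictive of a positive imaging study", and defines MFS by first M1 or death. None of these mentions the repeat scan. Section 8.3.1 left the complete list of candidate variables to the final SAP, and the SAP was not finalized, so no later document settles the matter.

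**The concern.** Sensitivity and specificity need both scans in patients who are negative as well as positive, and a truth to measure them against. Here the second scan is ordered because the first was positive. A report that took 7.6.15 at its word would publish accuracy figures that the data cannot support.

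The repeat scan does carry useful information: whether a conversion to M1 at a change of modality would also have been seen on the patient's original modality. A future positive scan in men who are M0 at baseline is a listed secondary objective (3.2), and 7.6.15 lets the investigator change modality at discretion. A change to a more sensitive scan can therefore create an event, and factors that prompt the change can look like predictors of metastasis. The plan collects the scan that would show how far this happens, but does not say how to analyse it.

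**Working it through.** The documents give no sensitivity, specificity, number of switchers or target number of pairs, so there is no stated figure to reproduce. The check is whether the planned data identify the quantities named in 7.6.15.

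**1. Which cells are filled**

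| | Previous modality + | Previous modality − |
|---|---|---|
| New modality + (first use) | observed | observed |
| New modality − | no repeat scan | no repeat scan |

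The estimable paired quantity is P(prev+ | new+) = n(+,+) / [n(+,+) + n(+,−)].

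**2. Site reading taken as truth.** Every pair is then M1 by the new scan. New-modality sensitivity is 100% by construction. No M1-negative patient has a pair, so specificity has no denominator for either method.

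**3. Truth treated as unknown.** Let π be the prevalence of M1, and Se and Sp the sensitivity and specificity of the new (n) and previous (p) modality. Assume the two scans are independent given true status.

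- P(new+, prev+) = π·Se_n·Se_p + (1−π)(1−Sp_n)(1−Sp_p)
- P(new+, prev−) = π·Se_n·(1−Se_p) + (1−π)(1−Sp_n)·Sp_p

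Set A (π = 0.32 borrowed from the baseline expectation in 8.1 for illustration only; the rest assumed): Se_n = Sp_n = 0.95, Se_p = 0.70, Sp_p = 0.90.

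- new+, prev+: 0.32×0.95×0.70 + 0.68×0.05×0.10 = 0.2128 + 0.0034 = 0.2162
- new+, prev−: 0.32×0.95×0.30 + 0.68×0.05×0.90 = 0.0912 + 0.0306 = 0.1218
- P(new+) = 0.338; P(prev+ | new+) = 0.2162/0.338 = 0.640
- The row with no repeat scan holds 0.662 of patients (0.076 new−/prev+ and 0.586 new−/prev−).

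Set B: π = 0.356, Se_n = 0.95, Sp_n = 1, Se_p = 0.64, Sp_p any value.

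- P(new+) = 0.356×0.95 = 0.338; P(prev+ | new+) = Se_p = 0.64

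The two sets give the same observable data. In A, 0.0306/0.1218 = 25% of discordant pairs are false positives on the new modality. In B none are, and Sp_p does not enter at all.

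A random search for all parameter sets matching both observables within 0.003 found these spans:

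| | Found | Searched |
|---|---|---|
| Se_n | 0.60–1.00 | 0.6–1 |
| Sp_n | 0.72–1.00 | 0.7–1 |
| Se_p | 0.64–1.00 | 0.4–1 |
| Sp_p | 0.50–1.00 | 0.5–1 |

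Three of the four fill or nearly fill the range searched. Se_p is bounded only from below, near the concordance itself. That bound arises because concordance is a weighted average of Se_p and 1−Sp_p, and the search held 1−Sp_p at or below 0.5.

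**4. Precision of what can be estimated.** Half-width = 1.96·√(0.64×0.36/n): 0.133 for n = 50 and 0.094 for n = 100. Both counts are assumed.

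**5. Where the repeat scan lands in Section 8**

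- *8.3.2, baseline-predictor logistic model and Cox model:* the event is set by the first-use positive, whatever the repeat scan shows.
- *8.3.2, all-scans model:* the repeat scan is a collected study, so it enters by default. Such records exist only where another scan was positive, and one man can contribute a positive and a negative within a month on nearly the same predictor values.
- *8.3.3, per-modality models:* scans are separated by modality and the pairing is not used.
- *8.3.3, MFS:* the first M1 counts, with no rule for M1 seen only on a newly adopted modality.

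**The case against.** **Accuracy is not a trial objective.** Comparing modalities for accuracy appears in no objective in 3.1 to 3.3 and no endpoint in Section 8; it is one clause explaining a procedure. This stands, and it limits the weight of the point.

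**Other pairs exist.** In 7.6.15 an equivocal standard bone scan is followed within a month by a more sensitive modality, whatever that second scan then shows. This stands as far as it goes, so it would be wrong to say that two-modality pairs arise only after a new-modality positive. These pairs are another selected group, with no independent truth, and do not rescue specificity.

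**The analysis does use the scan.** A reader might infer that Section 8 ignores it altogether. The documents do not support that: the all-scans model would absorb it, and the per-modality models could too. What is missing is a paired use and a handling rule.

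**The endpoint is working as defined.** The secondary objective is a positive scan, and M1 is whatever the site's modality shows. If the new modality gives no false positives, every unconfirmed first-use positive is real disease detected sooner. This stands: the planned endpoint is not an error and should remain the main analysis. It does not remove the case for showing how results depend on changes of modality.

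**Censoring at discovery of M1 is informative.** This stands. These men are at high risk, and they move to the M1 Phase, for which Table 1 schedules no imaging. Censoring also has no meaning in a logistic or GEE model. Any such analysis must be secondary, labelled, and specified separately for each model.

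**Conclusion.** The point holds in a limited form. The repeat scan cannot deliver the comparison given as its purpose in 7.6.15; it can deliver positive concordance among first-use new-modality positives. Section 8 plans no paired use of it and would let a record generated by a positive result into the all-scans model. The conclusion about accuracy follows from the trigger and the absence of a reference standard. It does not depend on the illustrative values, which only show how little the data constrain the parameters.

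A reader might go further and infer a size: divide an assumed previous-modality sensitivity by an assumed new-modality sensitivity (70/90 = 78%, say) and call the remainder events due only to the instrument. The documents do not support this. They give no modality sensitivities and no number of switchers, and 7.6.15 makes staying on the baseline modality the default. The ratio also ignores that these men had already been classed M0 on the previous modality. If, purely as an assumption, half of the new-modality positives were carried-over lesions that the previous modality goes on missing, confirmation would be 0.5×78% = 39%. The effect on the secondary endpoint and on MFS is therefore unquantified.

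This should be corrected, but it does not threaten the primary analysis: the primary endpoint is the baseline result, and the repeat scan arises only after a later change of modality.

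**What to change.** 1. **Section 7.6.15.** Restate the purpose as positive concordance among first-use new-modality positives. Report that proportion with a confidence interval, and make no claim about sensitivity or specificity.
2. **Section 8.3.2, all-scans GEE analysis.** Exclude the repeat scan triggered by a positive result as an outcome record.
3. **Sections 8.3.2 and 8.3.3.** Keep the planned M0 analyses as the main ones. Add a labelled sensitivity analysis for future M1 and for MFS in which a first-use positive with a negative paired previous-modality scan is not an M1 event: coded no in the logistic model, censored at that date in the Cox model. State beside the result that this censoring may be informative, because imaging on the original modality is not scheduled afterwards.

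The cost is a wording change, one exclusion rule and a re-run of planned models on data already collected. There are no extra scans and no change to patient management. The sensitivity analysis will have slightly fewer events. Because the SAP was not finalized, owing to insufficient data, the changes belong in the protocol text and in any report or reuse of this design. The claim about accuracy should be left out of a report whether or not the added analysis is feasible.
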